# 10.2 Investigation Endpoints

## 10.2.1 Primary performance endpoint

- Difference in sensitivity of pathological findings (pathological vs normal/no finding) between synthetic and conventional MR images on the full analysis set.
- Difference in specificity of pathological findings (pathological vs normal/no finding) between synthetic and conventional MR images on the full analysis set.

The ground truth is the site-determined diagnosis (pathological vs. normal/no finding).

#### 10.2.2 Secondary performance endpoints

- Difference in diagnostic accuracy of radiological findings (radiological finding class) between synthetic and conventional MR images on the subgroup of pathological patients. The ground truth is the site-determined diagnosis (radiological finding class).
- Primary and secondary endpoints (sensitivity, specificity, accuracy) in adults (18–99 years).
- Primary and secondary endpoints (sensitivity, specificity, accuracy) in pediatrics (0–17 years).

# 10.2.3 Exploratory endpoints

- Legibility of anatomical structures, per structure.
- Presence and type of artifacts, per contrast weighting (T1w, T2w).
- Inter-rater agreement (agreement, kappa coefficient and Gwet's AC1 coefficient) with regards to radiological finding classes.

	Clinical Investigation Code:	Date
SyntheticMR	CIP-003, Version K	2023-12-21

- Inter-method agreement (agreement, kappa coefficient and Gwet's AC1 coefficient) with regards to radiological finding classes.
- Image quality score per contrast weighting (T1w, T2w).

#### 10.2.4 Safety endpoints

• Incidence of Adverse Events (AE), Adverse Device Effects (ADE), Serious Adverse Events (SAE), Serious Adverse Device Effects (SADE), Unanticipated Adverse Device Effect (UADE), Unanticipated Serious Adverse Device Effect (USADE) and Device Deficiencies (DD).

# 10.3 Investigational Device(s) and Comparator(s)

#### 10.3.1 Investigational device - SyMRI 15 (3D)

SyMRI 15 (3D) will be used to post-process data from the 3D-QALAS acquisition to generate synthetic contrast weighted images with virtual scanner settings corresponding to the conventional images and thus generate synthetic T1w and T2w images. The post-processing will be carried out by the Sponsor and thus, neither the subjects nor the readers will be exposed to or handle the investigational device.

The comparator is conventional 3D MR images, which will be considered as ground truth in the investigation.

## 10.3.2 Other medical device to be used during the clinical investigation

All scanning will be done on 3.0T MRI machines from Philips. An investigational pulse sequence called 3D-QALAS from Philips will be used to generate the data necessary for SyMRI. This sequence is not yet cleared by FDA and will be provided to each site prior to investigation start via a research agreement between site and Philips.

# 10.4 Subjects

## 10.4.1 Inclusion Criteria

The subjects must meet all of the following criteria to be eligible to participate the investigation:

# **INCLUSION CRITERIA**

- 1 Any gender, aged 0-99 years
- 2 Subject scheduled for MRI of the brain

#### OR

Healthy control with passed screening form

- 3 | Subject suitable for MRI as judged by investigator
- 4 Subject agrees to 5-20 min extra MRI scan time
- 5 | Subject able to understand written and verbal information in English or Spanish
- 6 | Provision of informed consent (and assent if applicable)

#### 10.4.2 Exclusion Criteria

Subjects meeting any of the following criteria will not be permitted to participate in the investigation:

#### **EXCLUSION CRITERIA**

- 1 Have contraindication(s) to MRI scanning per the routine MR Safety Screening policy of the investigational site
- 2 Have severe trauma, disability or pre-existing pathology that is expected to interfere with normal conduct of MRI scanning or complete scanning of the brain
- 3 Have medical condition(s) such as those requiring urgent medical care that, in the opinion of a physician investigator, would prevent safe participation in the study
- 4 | Adult subjects (aged 18-99 years) in need of anesthesia during MRI scanning

	Clinical Investigation Code:	Date
SyntheticMR	CIP-003, Version K	2023-12-21

- 5 | Pregnancy at time of enrollment determined according to the clinic's MR Safety Screening policy
- **6** Previous enrollment in this investigation

#### 10.4.3 Relationship of Investigation Population to Target Population

SyMRI 15 (3D) is indicated for head imaging. The investigation population has been selected to represent the most common pathologies and abnormalities in the brain examined by MRI in the target population (see Section 7). Since SyMRI 15 (3D) is intended to be used in patients of all ages, subjects ranging from 0 to 99 years of age will be included in the investigation (see Section 20).

#### 10.4.4 Number of Subjects

In total 180 evaluable subjects will be recruited.

Approximately 120 will be patients, whereof 65 adult subjects (age 18-99 years) and 55 pediatric subjects (age 0-17 years). The pediatric population will consist of two groups, one with subjects receiving anesthesia (Sub-group Anesthesia) and one with subjects not receiving anesthesia (Sub-group No-anesthesia).

In addition, a group of approximately 60 evaluable, healthy adult controls will be included in the clinical investigation to be able to evaluate the specificity of the investigational device.

The aim is to include 5-14 subjects in each pathology group as specified in Table 4. The number of subjects per pathology groups is based on the prevalence of these pathologies (see Section 7.1). For the adult population, the aim is to include  $\geq 10$  subjects in the most common groups,  $\geq 5$  subjects in the intermediate group and  $\geq 3$  subjects in the least common groups. Corresponding figures for the pediatric group are  $\geq 7$  subjects in the most common groups,  $\geq 4$  subjects in the intermediate group and  $\geq 2$  subjects in the least common groups.

Prevalence was rated from 1 to 3 (1=most common, 2=common, 3=least common) as seen in Table 1 and Table 2.

Table 4: Target number of subjects per pathology group and sub-population

	Pediatric	population	Adult p	opulation	
		Target number		Target number	
Pathology group	Prevalence	of subjects	Prevalence	of subjects	Total
Infectious/Inflammatory/Demyelinating	2	≥ 4	1	≥ 10	≥ 14
Vascular Disorders of the Brain	2	≥ 4	1	≥ 10	≥ 14
Neuro Degenerative Disorders and Hydrocephalus	2	≥ 4	1	≥ 10	≥ 14
Intracranial Neoplasms	1	≥ 7	2	≥ 5	≥ 12
Traumatic Lesions	1	≥ 7	2	≥ 5	≥ 12
Congenital Malformations	2	≥ 4	2	≥ 5	≥9
Toxic and Metabolic conditions	3	≥ 2	3	≥ 3	≥ 5
Normal/no findings		N/A		N/A	

A Normal/no findings-category exists because some subjects are expected to present without any clinical findings.

Recruitment to the different pathology groups will be monitored during recruitment period. When the number of subjects in a pathology group is deemed sufficient by the Sponsor, recruitment to this specific group will be stopped to avoid overrepresentation of that pathology in the investigation population compared to the target population.

Each investigational site is estimated to recruit 20-30 patients. The healthy controls will be recruited by one of the investigational sites.

	Clinical Investigation Code:	Date
SyntheticMR	CIP-003, Version K	2023-12-21

A subject is defined as evaluable in the study if they have completed the necessary scans as described in this protocol. If a sequence is missing, or if settings did not follow the acquisition parameters (e.g resolution), or if the subject did not complete all scans, the subject images will be excluded from the image review.

# 10.4.5 Methods of Assigning Subjects to Different Treatment Arms

Not applicable since all subjects will undergo the same investigational procedures and no treatment is given to the subjects.

#### 10.4.6 Subject Withdrawal, Discontinuation, or Lost to Follow-up

Subjects are free to discontinue participation in the clinical investigation at any time and are not required to give a reason for their decision. However, subjects who discontinue the investigation should always be asked about the reason(s) for their discontinuation and about the presence of any adverse event (AE) /adverse device effect (ADE) and, if possible, be assessed by an investigator. Discontinuation from the clinical investigation will not affect the future treatment/care of the subject.

If the subject will withdraw his/her consent no further data will thereafter be recorded. Data collected up to the date of withdraw of informed consent will be used in the data analysis and for the Clinical Investigation Report (CIR). In case of withdrawal, all AEs/ADEs should be followed up.

Subjects may be withdrawn from the clinical investigation and assessments at any time, if deemed necessary by the Principal Investigator.

Specific reasons for withdrawal of subjects from this clinical investigation are:

- a) The decision of a subject to withdraw from the investigation (including if the subject withdraws informed consent);
- b) The Principal Investigator deems the subject unfit for the investigation or suspects poor CIP compliance;
- c) The subject is not able to lay still in the MRI, causing poor quality of the MRI scans;
- d) The Principal Investigator deems it is in the subject's best interest to be taken out of this investigation, e.g. due to claustrophobia.

Incorrectly enrolled subjects will be withdrawn from further assessments.

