The technology surrounding MRI is developing steadily, and newer quantitative techniques are now available to complement qualitative imaging, altogether resulting in more specific anatomical information. Recent progress in quantitative MRI makes it possible to measure physical properties of the human soft tissue, such as R1 and R2 relaxation rates and proton density (PD), on an absolute scale, altogether in a reasonable acquisition time. In other words, contrast varying synthetic MR images can be produced upon a single acquisition by calculating the expected image intensity with virtual contrast settings. Therefore, this technique may contribute to shortening the duration of the MRI exam. In addition, quantitative MRI approaches allow for a more objective and reproducible evaluation of the tissue than does conventional MRI, the assessment of which is based on the arbitrary signal contrast between tissues. However, the extensive acquisition time deployed to quantify these tissue parameters, and the potential emergence of motion artifacts are limitations that deserve to be considered. In this regard, motion artifacts could arise owing to the fact that the quality of synthetic MR images hinges on that of a single acquisition and that the patient's comfort may be impacted by long MR acquisition times.

The generation of synthetic MR images using SyMRI, which is most commonly based on the two-dimensional (2D) multi-dynamic multi-echo (MDME) sequence, has been previously validated for the brain and proven to be non-inferior to conventional MR images. For example, the MDME sequence has been used for the assessment of different brain diseases, including MS, brain infarctions, and meningitis, among others. However, this sequence, owing to its 2D properties, has a relatively low resolution in the slice direction compared to three-dimensional (3D) acquisition, fact that has likely hampered its use in routine clinical examination.

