#### 10.7.2.1.1 MRI Protocol

All MRI scans will be performed on a 3.0T MRI from Philips. For the investigation, images will be acquired using a fixed set of scanning parameters according to Table 6. The resolution will be similar for all sequences or as close as possible depending on MRI scanner.

Table 6: Acquisition	parameters fo	or 3D-QALAS i	and conventional .	sequences
----------------------	---------------	---------------	--------------------	-----------

Imaging Parameters	3D T1w	3D T2w	3D T2w FLAIR	3D-QALAS
FOV (mm)	220-250	220-250	220-250	220-250
Resolution	0.9-1.2 mm iso	0.9-1.2 mm iso	0.9-1.2 mm iso	1.2 mm iso
TR				Shortest
TE				2.3
TI	Site dependent	Site dependent	Site dependent	-
ETL				150
Bandwidth (Hz/px)				393
Acceleration technique	SENSE or CS-SENSE	SENSE or CS-SENSE	SENSE or CS-SENSE	CS-SENSE
Scan time (estimate)	2-4 min	2-4 min	3-6 min	5-6 min

Since this is a multi-site study with six sites, some difference in the image acquisition between the conventional images will need to be accepted. For example, resolution is allowed to range between 0.9-1.2 mm isotropic for the conventional images. FOV can vary depending on patient head size. Acceleration technique and amount of acceleration may also be different for conventional images from the different sites.

If any of these sequences are available in the standard protocol, with the requested resolution, this will be used as input for this clinical investigation. It is likely that some of these sequences with the specified resolution will need to be added after the routine clinical scan. This means that depending on the standard protocol used by the site for the specific clinical question, this may add an extra 1-4 sequences

	Clinical Investigation Code:	Date
SyntheticMR	CIP-003, Version K	2023-12-21

for the subject. The conventional 3D images can be generated with either Turbo Spin Echo sequences or Gradient Echo sequences, therefore all imaging parameters are not specified beforehand.

After completed MRI scan, subject ends his/her participation in the clinical investigation.

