#### 12 STATISTICAL CONSIDERATIONS

# 12.1 Statistical Design, Method and Analytical Procedures

#### 12.1.1 Analysis populations

- The full analysis set consists of all subjects with at least one pair of synthetic-conventional MR image readings from at least one reader.
- The pathological subgroup consists of all subjects with a pathological finding according to site-determined diagnosis.
- The control group consists of all non-pathological subjects, including both healthy volunteers and subjects classified as normal/no-finding according to site-determined diagnosis.
- The adult sub-population consists of all subjects aged 18–99 years.
- The pediatric sub-population consists of all subjects aged 0–17 years.

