# 12.10 Missing, Unused or Spurious Data

Available data from prematurely withdrawn subjects will be included in the analysis as far as possible. Only pairs of synthetic and conventional images evaluated by the same reader will be included in the analysis.

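### Could withdrawal for motion under section 10.4.6(c) keep complete, on-parameter scans out of image review and the full analysis set?

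*Combined protocol and SAP*

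**What the plan says.** Two sections of the combined protocol and SAP bear on whether a subject's images are read.

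- Section 10.4.4 (Number of Subjects): "A subject is defined as evaluable in the study if they have completed the necessary scans as described in this protocol". It removes images from review on three grounds: a sequence is missing, the settings departed from the acquisition parameters, or the scans were not all completed. Image quality is not a ground.
- Section 10.4.6 (withdrawal): "Subjects may be withdrawn from the clinical investigation and assessments at any time, if deemed necessary by the Principal Investigator". Reason (c) on its list is "The subject is not able to lay still in the MRI, causing poor quality of the MRI scans". No severity threshold, sequence or assessor is named, and nothing is said about images already acquired.

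Three further provisions settle what follows from a withdrawal.

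- Section 12.10: "Available data from prematurely withdrawn subjects will be included in the analysis as far as possible".
- Section 12.1.1: "The full analysis set consists of all subjects with at least one pair of synthetic-conventional MR image readings from at least one reader".
- Section 10.7.2.1.1: "After completed MRI scan, subject ends his/her participation in the clinical investigation". Consistently with this, section 10.4.7 provides no follow-up, section 10.6 gives one day of participation, and Table 5 records subject termination at Visit 1.

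**The concern.** A subject can complete all four sequences on-parameter and still have moved. Such a subject is evaluable under 10.4.4 and can apparently also be withdrawn under 10.4.6(c). No sentence says which rule prevails. If withdrawal meant that the images were not sent to the readers, there would be no pair of readings and the subject would leave the full analysis set without any analysis rule having been applied.

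That would be selection on image quality, and the plan gives a reason to think that quality may not affect the two methods alike. Section 5.1 notes that "the quality of synthetic MR images hinges on that of a single acquisition", and both synthetic contrasts are computed from one 3D-QALAS run. Leaving out motion-degraded sets might therefore flatter the synthetic images in a non-inferiority comparison with a margin of 0.05. The same sets are informative for the exploratory artifact and image-quality endpoints of section 10.2.3. The plan specifies no table that would show whether any had been left out.

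**Working it through.** **1. The plan's own figure.** Section 12.4 gives 90% power for each primary endpoint and 80% for both. Under independence, 0.90 × 0.90 = 0.81; the lower bound without independence is 1 − 0.10 − 0.10 = 0.80. The stated 80% is reproduced. The total of 180 cannot be rebuilt, because the accuracy and correlation assumptions are not in the available text; that is not counted against the plan.

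**2. The rules side by side, for a complete, on-parameter set with motion.**

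| Section | What it governs | Effect on this set |
|---|---|---|
| 10.4.4 | Which images are excluded from review | None of its three grounds applies, so the set is reviewed |
| 10.4.6(c) | Whether a subject may be withdrawn | Permissive; does not say that acquired images are discarded |
| 12.10 | Withdrawn subjects' data | Kept as far as possible |
| 12.1.1 | Full analysis set | Requires a reading pair; does not exclude withdrawn subjects |
| 10.7.2.1.1, 10.4.7, Table 5 | When participation ends | At scan completion, so little remains to be withdrawn from afterwards |
| 10.7.5.2, 10.7.5.4 | What readers record | Motion is a listed artifact; the quality scale runs down to its lowest grade of 1 |

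To lose the set, one must add a step that no section contains: that withdrawal also blocks upload or reading.

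**3. What the selection could act on.** Withdrawal is the investigator's decision. Sites do not see synthetic images (8.2), and the sponsor generates them only after recruitment is complete (6.3). An investigator can notice motion but cannot select on the synthetic result. The direction is open:

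- Section 6 claims better registration for a single acquisition, because there is no movement between acquisitions.
- Table 3 says that motion artifacts are common in conventional MR too.
- Scan times in Table 6 are similar: 3D-QALAS 5–6 min, against 2–4 plus 2–4 = 4–8 min for conventional T1w and T2w together.
- The same conventional FLAIR is read with both image types (10.7.3.2).

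**4. Size, if sets were nevertheless left out.** Let n be the retained subjects, k the complete sets left out, and L the extra loss of synthetic accuracy (relative to conventional) in those sets compared with the retained ones. Restoring them moves the estimated difference by

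shift = −L × k/(n + k), so the number needed for a shift of size s is k = n × (s/L)/(1 − s/L).

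The documents give neither k nor L; both are assumed. For each primary endpoint n = 90 (section 12.2). With k = 3, k/(n + k) = 3/93 = 0.032, and the shift is +0.003 at L = −0.10, 0 at L = 0, −0.003 at L = 0.10 and −0.006 at L = 0.20.

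| Sets needed, rounded up | L = 0.10 | L = 0.20 |
|---|---|---|
| n = 90, s = 0.01 | 90 × 0.1/0.9 = 10 | 90 × 0.05/0.95 = 4.74, so 5 |
| n = 90, s = 0.025 | 90 × 0.25/0.75 = 30 | 90 × 0.125/0.875 = 12.86, so 13 |
| n = 32, s = 0.01 | 3.56, so 4 | 1.68, so 2 |
| n = 32, s = 0.025 | 10.67, so 11 | 4.57, so 5 |

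The 32 is the sum of the pediatric minima in Table 4 (4 + 4 + 4 + 7 + 7 + 4 + 2). It is a floor: 55 pediatric patients are planned.

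**5. Power.** Suppose that 5 of the 90 in one group went unread and were not replaced. With a true difference of 0 and variance proportional to 1/n, power for that endpoint is Φ(3.2415 × √(85/90) − 1.960) = 88.3%, and joint power is 0.883 × 0.90 = 79.5%, against 81.0% with none lost.

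**The case for a change.** The best case for a change runs as follows. Reason (c) is worded on scan quality, not on an unfinished scan, and 10.4.6 allows withdrawal at any time. If (c) covered only unfinished scans, 10.4.4 would already exclude those images and (c) would add nothing. Section 12.10 hedges, and it does not say that a withdrawn subject's images go to readers. The firmer sentence in 10.4.6, that data already collected will be used, is tied to withdrawal of consent. One sentence and one table would close the matter cheaply before reading starts.

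Part of this stands: no sentence says expressly that such a set is read, and the wording of 12.10 is loose. The redundancy argument is weaker than it looks. Withdrawing a subject and excluding images are different acts: (c) gives a reason for ending a subject's part, while 10.4.4 says what becomes of the images, so both have work to do when a scan is abandoned for motion. Reason (c) also stands beside claustrophobia, which arises during the scan. And if collected data are kept even when consent is withdrawn, discarding them after a withdrawal for motion would be an odd reading.

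The risk in section 9.6 does not strengthen the case. It concerns novel artifacts specific to the device, whereas Table 3 treats patient movement separately as well known.

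As to the table, subject termination, conformity of the MRI with the protocol and use of anesthesia are already recorded (Table 5, 10.7.4), and reasons for discontinuation are sought (10.4.6). Section 22 ties the final report to an ISO annex whose content is not available here, so it cannot be shown that exclusions would go unreported.

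**Conclusion.** No change to the plan follows. This is missing detail that analysts would fill sensibly: on an ordinary reading, a complete, on-parameter set goes to review whatever its motion, and once read it belongs to the full analysis set. No stated number, rule or conclusion is shown to be wrong.

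The possible effect on the primary endpoints is small unless many sets are lost. Half the margin would need 13 sets at L = 0.20 or 30 at L = 0.10, beside 90 retained, and the sign of L is itself unknown. Pediatric sensitivity is more exposed, at 5 or 11 sets on the Table 4 floor. It is, however, fifth in the fixed secondary sequence (section 12.1.4) and outside the pass criterion (section 12.5).

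The conclusion rests on reading 10.4.4 as the rule that governs review and (c) as directed at scans that fail while under way. The sizes rest on assumed values of k and L. Nothing in the documents shows that any completed set was held back for motion.

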#### 10.4.7 Subject Follow-up and Care

After completed MRI scan, there is no follow-up of the subjects within the investigation. Instead, subjects will be treated according to site's clinical routine.

# 10.5 Readers

All readers participating in the image review part of the study will have more than 10 years of post-graduate experience within neuroradiology. All readers will be US ABR and CAQ certified neuroradiologists.

The readers will be blinded to site-determined diagnosis to reduce information bias.

The following information will be collected from all readers: Name, Country, Job Title, Fellowship status, Practice focus, Years of experience (post-graduate), CV and Certificates.

